7.2.2.3 Transfusion Data

Details of all blood products and haemostatic agents released from the blood bank/pharmacy and transfused will be collected from the blood bank/pharmacy databases. These include allogeneic blood components (RBCs, pooled or apheresis platelets and plasma) and albumin. Other haemostatic agents include: desmopressin, fibrinogen concentrates, cryoprecipitate, rFVIIa, antithrombin, idarucizumab and andexanet alpha. Data collected will be used for a pharmacoeconomic analysis to be conducted at a later date.

7.2.2.4 Bleeding Data

Severity of bleeding before IMP administration according to the Bleeding Severity Scale by Lewis et al [78] will be collected during surgery.

The comparison of 'major' bleeding based on the universal definition of perioperative bleeding (UDPB) in cardiac surgery [89, 93] (**Table 5**Error! Reference source not found.) will be assessed. The UDPB is a multistage definition for perioperative bleeding based on easily measured clinical endpoints, including total blood loss from chest tubes at 12 hours and 24 hours after chest closure, allogeneic blood components transfused, surgical re-exploration including cardiac tamponade, delayed sternal closure and the need for salvage treatment. Modifications to the UDPB will include addition of fibrinogen concentrate to cryoprecipitate and exclusion of the category of delayed sternal closure.

Depending on these components, bleeding is graded as insignificant, mild, moderate, severe or massive (**Table 5**Error! Reference source not found.) [89].

Intracerebral and gastrointestinal haemorrhages will be documented.

Table 5: Bleeding categories according to the UDPB in adult cardiac surgery (if different categories indicate mixed definitions of bleeding, the worst definition applies) [89]

Bleeding definition	Postoperative chest tube blood loss within 12 h (mL)	RBC (units)	FP (units)	PLT (units)	Fibrinogen concentrate or Cryoprecipitate	PCC	rFVIIa	Re-exploration/tamponade
Class 0 (insignificant)	<600	0	0	0	No	No	No	No
Class 1 (mild)	601–800	1	0	0	No	No	No	No
Class 2 (moderate)	801–1000	2–4	2–4	Yes	Yes	Yes	No	No
Class 3 (severe)	1001–2000	5–10	5–10	N/A	N/A	N/A	No	Yes
Class 4 (massive)	>2000	>10	>10	N/A	N/A	N/A	Yes	N/A

FP, frozen plasma; N/A, not applicable; PCC, prothrombin complex concentrate; PLT, platelets; rFVIIa, activated recombinant factor VII; UDPB, universal definition of perioperative bleeding.

To remove any potential bias from PCC and/or FP dosing, as their use is dictated by the randomisation schedule, a modified version of the UDPB will also be applied, with the following components of the score omitted: administration of PCC and transfusion of FP.

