
3. Severe right heart failure (clinical diagnosis ± echocardiography)
 
4. Known contraindications to heparin
 
5. PCC required for reversal of warfarin or direct oral anticoagulant (DOAC; dabigatran, rivaroxaban, apixaban or edoxaban) within 3 days prior to or during surgery
 
6. Known thromboembolic event (TEE) within 3 months prior to surgery
 
7. History of severe allergic reactions to PCC or FP
 
8. Individuals who have immunoglobulin A (IgA) deficiency with known antibodies against IgA
 
9. Refusal of allogeneic blood products
 
10. Known pregnancy
 
11. Currently enrolled in other interventional clinical trials

Test Product, Dose and Mode of Administration: Octaplex and FP will be administered intravenously. For the first ordered dose, the blood bank/pharmacy will prepare and release either Octaplex or FP, as per the randomised group allocation. The dose for Octaplex will be 1500 IU for patients weighing ≤60 kg and 2000 IU for patients weighing >60 kg. The dose for FP will be 3 U for patients weighing ≤60 kg and 4 U for patients weighing >60 kg). If a second order of coagulation factors is received during the treatment period of 24 hours after IMP initiation, the blood bank/pharmacy will release a second dose of Octaplex or FP as above. The maximum allowable dose of IMP will be: Octaplex 3000 IU if ≤60 kg or 4000 IU if >60 kg; FP 6 U if ≤60 kg or 8 U if >60 kg. If further doses of coagulation factors are required, non-IMP FP will be administered. That is, once the maximum dose of IMP (i.e., two doses) has been administered, if additional amounts of coagulation factors are ordered during the treatment period, and for any requests after the treatment period, the blood bank/pharmacy technologist will release FP (in 1–4 U increments at the discretion of the ordering physician) for both groups; these additional FP units will not be counted as part of the IMP.
Duration of Treatment: Twenty-four hours from IMP initiation or until the maximum dose of the IMP has been administered, whichever occurs first.

Name of Sponsor/Company: Octapharma AG	
Name of Investigational Product: Octaplex	Protocol Identification Code: LEX-211
Name of Active Ingredient: Prothrombin complex concentrate, human	Date of Final Protocol: 25-Aug-2023

Reference Therapy, Dose and Mode of Administration:

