### 10.3. Secondary Endpoints

The following secondary efficacy endpoints will be explored:

- S1. Comparison of global haemostatic response to *Octaplex* versus FP, defined as 'positive' if no additional haemostatic intervention (as per the primary endpoint) is required and haemoglobin levels decrease by <30% (after accounting for red cell transfusions) from 60 minutes to 24 hours after initiation of the first dose of IMP. The 24-hour haemoglobin result will be reduced by 1 g/dL for each unit of RBC transfused from 60 minutes to 24 hours.
- S2. Comparison of the total amount of chest tube drainage at 12 and 24 hours after chest closure between the *Octaplex* and FP groups.
- S3. Comparison of the incidence of severe to massive bleeding, using a modification of the universal definition of perioperative bleeding (UDPB) in cardiac surgery and its individual components during the first 24 hours after start of surgery, after the end of CPB and after IMP initiation, between the *Octaplex* and FP groups.
- S4. Comparison of the mean number of total allogeneic blood components – including red cells, platelets and all (IMP and non-IMP) FP – administered during the first 24 hours after the end of CPB, between the *Octaplex* and FP groups.
- S5. Comparison of the mean number of total non-IMP allogeneic blood components – including red cells, platelets and non-IMP FP – administered during the first 24 hours after the end of CPB, between the *Octaplex* and FP groups.
- S6. Comparison of the mean number of total non-IMP allogeneic blood components – including red cells, platelets, cryoprecipitate and non-IMP FP – administered during the first 24 hours and 7 days after IMP initiation, between the *Octaplex* and FP groups.
- S7. Comparison of the mean number of individual allogeneic blood components – including red cells, platelets, cryoprecipitate and non-IMP FP – administered during the first 24 hours and 7 days after the start of surgery, after the end of CPB and after IMP initiation, between the *Octaplex* and FP groups.
- S8. Comparison of the incidence of transfusion of individual allogeneic blood components – including red cells, platelets, cryoprecipitate and non-IMP FP – during the first 24 hours and 7 days after the start of surgery, after the end of CPB and after IMP initiation, between the *Octaplex* and FP groups.

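### S3 (severe to massive bleeding) is not tied to either of the protocol's two UDPB versions, and the one its wording favours scores a second plasma dose as severe but a second PCC dose as at most moderate on the product columns

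*Protocol*

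**What the plan says.** Protocol 7.2.2.4 grades bleeding from class 0 to class 4 on several components, and the worst component decides the class (Table 5 title). The two rows that matter here read "Class 2 (moderate) 801–1000 2–4 2–4 Yes Yes Yes No No" and "Class 3 (severe) 1001–2000 5–10 5–10 N/A N/A N/A No Yes". The columns run in this order: 12-hour chest tube loss, RBC, FP, platelets, fibrinogen concentrate or cryoprecipitate, PCC, rFVIIa, re-exploration/tamponade.

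The section makes two sets of changes to the published score. The first is: "Modifications to the UDPB will include addition of fibrinogen concentrate to cryoprecipitate and exclusion of the category of delayed sternal closure". That set leaves FP units and PCC in. The section then closes by saying that, because randomisation dictates PCC and FP use and this may cause bias, "a modified version of the UDPB will also be applied", with PCC administration and FP transfusion left out.

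S3 in SAP 10.3 is worded as "Comparison of the incidence of severe to massive bleeding, using a modification of the universal definition of perioperative bleeding (UDPB) in cardiac surgery", together with its individual components, over 24-hour windows counted from three starting points. Protocol 3.1.2 and SAP 5.2 use the same wording. SAP 10.3 compares the S3 proportions by logistic regression. SAP Appendix 1, which lists derived variables, has no UDPB entry.

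**The concern.** In the FP arm the study treatment is itself a scored item of the bleeding scale, and it is scored in units. In the PCC arm the study treatment is scored yes or no, and that column stops at moderate. A patient given a second dose of the assigned product can therefore cross into severe in one arm but not in the other, with the same blood loss, red cell use and re-exploration status.

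The protocol recognises this and plans a score without the two products, but it does not say that S3 is that score. A programmer working from the SAP could build S3 either way. If S3 is built on Table 5, its proportions, odds ratio and p-value partly reflect which product was allocated. If the choice is left until results are known, there are two versions to choose from, and their results can differ by construction.

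**Working it through.** **Inputs**

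- FP per order (protocol synopsis, dosing): "The dose for FP will be 3 U for patients weighing ≤60 kg and 4 U for patients weighing >60 kg".
- FP counted as IMP over two doses (protocol synopsis and 3.2): "FP 6 U if ≤60 kg or 8 U if >60 kg".
- PCC per order (same places): the dose "will be 1500 IU for patients weighing ≤60 kg and 2000 IU for patients weighing >60 kg".
- Class limits: the Table 5 rows quoted above, plus class 4, which is more than 10 U of FP, with PCC not applicable.

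**Reproducing the stated maximum.** FP: 2 × 3 = 6 U and 2 × 4 = 8 U, as stated. PCC: 2 × 1500 = 3000 IU and 2 × 2000 = 4000 IU, as stated.

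**Class from the randomised product alone**

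| IMP received | FP arm, Table 5 | PCC arm, Table 5 | Either arm, PCC and FP omitted |
|---|---|---|---|
| One full dose | 3–4 U: class 2 | PCC given: class 2 | no contribution |
| Two full doses | 6 or 8 U: class 3 | PCC given: class 2 | no contribution |

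The arms are level after one dose and part at the second. A third order can widen the gap. In a patient over 60 kg, 8 U of IMP plus 3–4 U of non-IMP FP makes 11–12 U, which is class 4. The same three orders in the PCC arm give 3–4 U of FP, which is class 2.

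With the two product columns omitted, class 3 or higher depends only on chest tube loss, RBC, rFVIIa or re-exploration/tamponade, and the asymmetry from randomised product is zero.

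**Size of the artefact.** The documents give no second-dose rate, so both inputs below are assumptions:

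- r is the share of patients whose second dose is given in full, equal in both arms.
- q is the share of those patients who are already class 3 or higher on other components, also equal in both arms.

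Among second-dose patients, the FP arm contributes r to the severe proportion and the PCC arm contributes rq. The artefactual difference (FP minus PCC) is r − rq = r(1−q), in percentage points:

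| r | q = 75% | q = 50% | q = 25% |
|---|---|---|---|
| 5% | 1.25 | 2.5 | 3.75 |
| 10% | 2.5 | 5.0 | 7.5 |
| 20% | 5.0 | 10.0 | 15.0 |
| 30% | 7.5 | 15.0 | 22.5 |

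**What the pilot adds.** Protocol 1.1 reports that 4 of 47 FP patients needed more than two FP doses: 4/47 = 8.5% (95% CI 2.4–20.4%). The pilot used the same doses (protocol 1.2), so with full doses each of these patients passes 5 U. The figure shows who would meet the FP threshold by dose. It does not show how many would be misclassified, because some would be severe on other components. In the PCC arm, 2 of 54 (3.7%) needed FP after PCC.

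**The case against.** A reader might infer that S3 as defined counts the randomised plasma. The documents do not support that. S3 says only that a modification is used, and the closing sentence of protocol 7.2.2.4 also describes a modified version, so S3 may already be the score without PCC and FP. The protocol names the bias and plans the remedy, so no analysis is missing. SAP 4.4 refers to protocol 7.1 to 7.3 for assessments, SAP 14 says that the analyses match the protocol, and S3 reports individual components, so an effect driven by FP units would be visible. This stands, except that the SAP cross-reference brings in both versions without choosing one. The protocol's wording also leans the other way: its explicit list of modifications keeps both products, and the version without them is introduced as an addition.

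A reader might also infer that a second FP dose makes a patient severe whatever the bleeding. That is too strong. A second dose requires continuing bleeding of at least moderate grade, and doses may be partial (SAP Table 1 provides for this). Randomisation fixes the product, and bleeding drives whether more is given. The difference between arms remains, but the class is not independent of bleeding. Nor are two PCC doses capped at moderate overall: drainage, red cells, rFVIIa, re-exploration or 5 U or more of non-IMP FP can raise the class.

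Finally, S3 is one of 15 secondary efficacy endpoints that SAP 10.3 treats as exploratory, and no confirmatory claim rests on it. That stands and limits the weight of the point.

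**Conclusion.** The concern holds as a gap in definition with a known direction of bias. S3 is not fixed to either UDPB version, the protocol's wording favours the version that counts the randomised products, and the SAP is silent on the other. On the Table 5 version, the comparison favours PCC partly by construction from the second full dose onwards. This follows directly from the stated doses and class limits.

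The size cannot be computed from the documents. The r(1−q) figures rest on assumed values of r and q that are equal in both arms and on full second doses, so they illustrate scale and do not estimate it. The pilot's 8.5% should not be read as a misclassification rate.

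The primary non-inferiority and superiority tests are unaffected. The point is still worth acting on, because the protocol itself identifies the bias and S3 carries a formal between-group comparison. The plan already separates IMP from non-IMP plasma in S5 and S6, so S3 is the place where this separation was left open.

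**What to change.** In SAP 5.2 and 10.3, define S3 as UDPB class 3–4 with the PCC and FP components omitted, as protocol 7.2.2.4 already provides. In Appendix 1, add the derivation: the components kept, their class limits, the worst-component rule and the three time windows. Report the Table 5 version as a supportive table, with a footnote saying that it is affected by allocation.

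The cost is SAP wording and one derivation. Both versions are already planned, so no new data are needed. The change should be made before database lock, so that the choice cannot depend on results.

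There is one small downside. The protocol omits FP transfusion without restriction, so non-IMP rescue plasma also drops out, and a patient in either arm whose only severe component is 5 U or more of rescue plasma would no longer count as severe. The supportive table and the individual components still show those patients.

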7.3 Safety Assessments

7.3.1 Assessments for Safety Endpoints

Any of the following drug safety information shall be collected:

- AEs and SAEs temporally associated with the administration of IMP (for definitions and reporting requirements, see **Sections 7.3.2, 7.3.3 and 7.3.4**).
- Pregnancies, drug overdose, interaction, medication error, lack of efficacy and post-study SAEs (see **Section 7.3.6**).

7.3.2 Adverse Events (AEs)

7.3.2.1 Definitions

- **Adverse event (AE):** An AE is any untoward medical occurrence in a study patient receiving an IMP and which does not necessarily have a causal relationship with this treatment. An AE can therefore be any unfavourable and unintended sign (including an abnormal laboratory finding), symptom or disease temporally associated with the use of an IMP, whether or not related to the IMP. An AE is defined as a treatment-emergent AE (TEAE) if first onset or worsening is after the first treatment with study drug.
- **Adverse drug reaction (ADR):** An ADR is any noxious and unintended response to an IMP related to any dose. The phrase 'response to an IMP' means that a causal relationship between the IMP and an AE carries at least a reasonable possibility, i.e., the relationship cannot be ruled out.

- **Other significant AEs:** Any marked laboratory abnormalities or any AEs that lead to an intervention, including withdrawal of drug treatment, dose reduction or significant additional concomitant therapy.
- **Withdrawal due to AE/ADR:** AE/ADR leading to discontinuation of treatment with IMP. Any such events will be followed up by the Investigator until the event is resolved or until the medical condition of the patient is stable. All follow-up information collected will be made available to the Sponsor.

7.3.2.2 Collection of AEs

The condition of the patient will be monitored throughout the study. At each visit, whether scheduled or unscheduled, AEs will be elicited using a standard non-leading question such as "How have you been since the last visit/during the previous study period?" In addition, the Investigator/blinded outcome assessor will check the patient records for any documented event.

Any AE or ADR which occurs during the study will be noted in detail on the appropriate pages of the CRF. If the patient reports several signs or symptoms representing a single syndrome or diagnosis, the diagnosis should be recorded in the CRF. The Investigator will grade the severity of all AEs or ADRs (mild, moderate or severe), the seriousness (non-serious or serious) and the causality as defined below. The Sponsor is responsible for assessing the expectedness of each ADR (expected or unexpected) as defined below.

In the event of clinically significant abnormal laboratory findings, the tests will be confirmed and the patient followed up until the laboratory values have returned to normal and/or an adequate explanation for the abnormality has become available.

Diseases, signs and symptoms and/or laboratory abnormalities already present before the first administration of IMP will not be considered AEs unless an exacerbation in intensity or frequency (worsening) occurs.

The Investigator will provide detailed information about any abnormalities and about the nature of and reasons for any action taken, as well as any other observations or comments that may be useful for the interpretation and understanding of an AE or ADR.

7.3.2.3 Severity of AEs

The intensity/severity of AEs will be graded as follows:

- **Mild:** an AE, usually transient, which causes discomfort but does not interfere with the patient's routine activities
- **Moderate:** an AE which is sufficiently discomforting to interfere with the patient's routine activities
- **Severe:** an AE which is incapacitating and prevents the pursuit of the patient's routine activities

The grading of an AE is up to the medical judgement of the Investigator and will be decided on a case-by-case basis.

7.3.2.4 Causality of AEs

The relationship of AEs to the administered IMP will be assessed by the Investigator:

- **Probable:** reports including good reasons and sufficient documentation to assume a causal relationship, in the sense of plausible, conceivable, likely, but not necessarily highly probable. A reaction that follows a reasonable temporal sequence from administration of the IMP; or that follows a known or expected response pattern to the suspected medicine; or that is confirmed by stopping or reducing the dosage of the medicine and that could not reasonably be explained by known characteristics of the patient's clinical state.
- **Possible:** reports containing sufficient information to accept the possibility of a causal relationship, in the sense of not impossible and not unlikely, although the connection is uncertain or doubtful, for example because of missing data or insufficient evidence. A reaction that follows a reasonable temporal sequence from administration of the IMP; that follows a known or expected response pattern to the suspected medicine; but that could readily have been produced by a number of other factors.
- **Unlikely:** reports not following a reasonable temporal sequence from IMP administration. An event which may have been produced by the patient's clinical state or by environmental factors or other therapies administered.
- **Not related (unrelated):** events for which sufficient information exists to conclude that the aetiology is unrelated to the IMP.
- **Unclassified:** reports which for one reason or another are not yet assessable, e.g., because of outstanding information (can only be a temporary assessment).

7.3.2.5 Classification of ADRs by Expectedness

ADRs will be classified by the Sponsor as either expected or unexpected:

- **Expected:** an ADR that is listed in the current edition of the Investigator's Brochure (IB) or other reference safety information.
- **Unexpected:** an ADR that is not listed in the current edition of the IB or other reference safety information, or that differs because of greater severity or greater specificity.

7.3.2.6 Outcome of AEs

The outcome of all reported AEs has to be documented as follows:

1. Recovered, resolved
2. Recovering, resolving
3. Not recovered, not resolved
4. Recovered, resolved with sequelae
5. Fatal
6. Unknown

NOTE: A patient's **death** per se is not an event, but an outcome. The event which resulted in the patient's death must be fully documented and reported, even in cases where the

death occurs within 4 weeks after IMP treatment end and regardless of whether or not it is considered treatment related.

7.3.2.7 Action(s) taken

AEs requiring action or therapy must be treated with recognised standards of medical care to protect the health and well-being of the patient. Appropriate resuscitation equipment and medicines must be available to ensure the best possible treatment in an emergency situation.

The action taken by the Investigator must be documented:

a) General actions taken in the event of an AE

- None
- Medication (other than IMP) or other (e.g., physical) therapy started
- Test performed
- Other (to be specified)

b) IMP-related actions taken in the event of an AE

- None
- Product withdrawn
- Dose reduced
- Dose increased

The Investigator will follow up on each AE until it has resolved or until the medical condition of the patient has stabilised. Any relevant follow-up information will be reported to the Sponsor.

7.3.3 Serious Adverse Events (SAEs)

Standard statement:

A **serious AE (SAE)** is any untoward medical occurrence that at any dose:

- results in death,
- is life-threatening (see below),
- requires hospitalisation or prolongation of existing hospitalisation,
- results in persistent or significant disability/incapacity,
- is a congenital anomaly/birth defect,
- is another important medical event.

NOTE: The term 'life-threatening' refers to an event in which the patient was, in the view of the reporting Investigator, at immediate risk of death at the time of the event; it does not refer to an event which may hypothetically have caused death had it been more severe.

In deciding whether an AE/ADR is serious, medical judgment should be exercised. Thus, important AEs/ADRs that are not immediately life-threatening or do not result in death or hospitalisation but may jeopardise the patient or may require intervention to prevent one of the other outcomes listed in the definitions above should also be considered serious.

In addition, although not classified under the seriousness criteria, all suspected transmissions of an infectious agent should be reported as SAEs. A suspected virus transmission means that virus antigen has been detected in the patient. A passive transmission of antibodies alone does not constitute a suspected virus transmission.

